2. OBJECTIVES

2.1. Primary objective

To determine the recommended phase II dose (RP2D), the maximum tolerated dose (MTD) evaluated on the first 21 days (D1 to D21), the safety profile and the dose limiting toxicities (DLT) of trabectedin given in combination with durvalumab in patients with advanced pretreated soft-tissue sarcoma and ovarian carcinoma.

2.2. Secondary objectives

- To evaluate the toxicity profile of trabectedin in association with durvalumab (NCI-CTCAE v4.03)
- To determine preliminary signs of anti-tumor activity of trabectedin given in combination with durvalumab in two expansion cohorts (STS and ovarian carcinomas) in terms of :
 - Best overall response as per RECIST v1.1,
 - objective response under treatment as per RECIST v1.1,
 - 6-month objective response as per RECIST v1.1,
 - 6-month progression-free status defined as per RECIST v1.1,
 - 1-year progression-free survival (PFS),
 - 1-year overall survival (OS).
- To explore the pharmacodynamics (PD) of Trabectedin in association with Durvalumab as well as potential predictive biomarkers of activity and efficacy (blood and tumor tissue samples).

3. STUDY DESIGN

3.1. OVERALL STUDY DESIGN

This is a multicenter, prospective open-labeled phase Ib trial based on a dose escalation study design (3+3 traditional design) assessing three dose levels of trabectedin given in combination with durvalumab, followed by two expansion cohorts (STS and ovarian carcinomas) once the MTD has been established.

3.2. DEFINITIONS

Dose-limiting toxicity (DLT):

A DLT is defined as an AE or laboratory abnormality that fulfills all the criteria below:

- Begins on the first 21 days of treatment.
- Is considered to be at least possibly related to the study treatment.
- Meets one of the criteria below, graded as outlined or according to NCI-CTCAEv4.03 :
 - Any grade-4 toxicity (except for vomiting without maximal symptomatic/prophylactic treatment and if toxicity is transaminitis, but which have to be resolved at Day 21, i.e. return to Baseline or grade 1).
 - Grade-3 non-haematological toxicity lasting > 7days (except for 1rst episode of nausea and if toxicity is transaminitis, which have to be resolved at Day 21, i.e. return to Baseline or grade 1).
 - Grade-3 hematologic toxicity lasting for > 7days.
 - Grade 4 neutropenia with fever.
 - Grade > 2 thrombocytopenia with bleeding.

DLT status:

In addition, the steering committee will resolve any specific issue regarding the DLT status (see section 12.1.1).

Maximum tolerated dose (MTD):

The MTD is defined as the highest dose at which no more than 1 in 6 patients in the cohort experience a DLT in the first 21 days. The conclusions of the steering committee for the definition of

of the MTD will be submitted for approval to an independent data monitoring committee (IDMC) before opening the expansion cohorts.

Recommended phase II dose (RP2D):

The RP2D dose corresponds to the dose level to be recommended for further investigations in phase II trials. The RP2D dose for trabectedin when given in combination with Durvalumab, will be identified by the steering committee based on safety data from patients included in the dose escalation part and the expansion cohorts, as well as PD data. Data from all patients (dose escalation trial and expansion cohorts) will be used to define the RP2D.

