1.3.3. Clinical data

Trabectedin is approved in Europe for the treatment of patients with advanced soft-tissue sarcoma (STS) after failure of anthracyclines and ifosfamide, or when they are not eligible to receive these agents. In this setting, the 6-month progression-free rate is about 35-40% [12-16].

Recently, Le Cesne et al [49] published a retrospective pooled analysis of trabectedin safety in 1132 patients with solid tumors enrolled in 19 worldwide phase II trials from 1998 to 2008, in order to summarize the safety experience of single agent trabectedin. Three schedules of administration were considered: 24-hour infusion every 3 weeks, 3-hour infusion every 3 weeks and 3-hour infusion for three consecutive weeks every 4 weeks. Tolerance was good in phase II development, with a rate of toxic death of 1.7%. Neutropenia (69.2%) and thrombocytopenia (36.3%) were the most frequent drug-related toxic events. The incidence and severity of neutropenia were higher with the q3wk 24-h schedule, grade 3 in 26.6% and grade 4 in 23.9% of patients. Of note, prophylactic use of granulocyte colony stimulating factor (G-CSF) was generally not permitted in the trabectedin trials and, therefore, only administered to 9.8% of the patients. Other common trabectedin-related adverse events reported in at least 20% of patients were nausea (64.7%), fatigue (58.3%), and vomiting (40.1%).

Transaminase increase was common with trabectedin, with a peak elevation at days 5-7 and a return to grade ≤ 1 at approximately day 15 of each cycle. Dexamethasone was routinely administered to improve tolerance, including hepatic toxicity, and was given prior to infusion at the recommended dose of 20 mg 30 min before trabectedin in the majority of clinical studies. Rhabdomyolysis was uncommon (0.8%).

Extravasation-related AEs following injection were rare (6 out of 1132 patients, 0.5%), and only 3 of these events were serious or treatment limiting (grade 4). The use of a central-line was mandatory in the clinical trials.

No cumulative toxicities were apparent and trabectedin was able to be administered for prolonged periods (up to 59 cycles) to patients who exhibited sustained clinical benefit from stable disease or objective responses.

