- Adverse event that, in the opinion of the investigator or the sponsor, contraindicates further dosing,
- Subject is determined to have met one or more of the exclusion criteria for study participation at study entry and continuing investigational therapy might constitute a safety risk,
- Pregnancy or intent to become pregnant,
- Grade ≥ 3 infusion reaction,
- Initiation of alternative anticancer therapy including another investigational agent,
- Intercurrent illness of sufficient magnitude to preclude safe continuation of the study,
- Patient refusal and/or non compliance with study requirements,
- Protocol deviation with an effect on the risk/benefit ratio of the clinical trial

Patients still experiencing a non-progression after 6 cycles will then be able to continue treatment off-study at the discretion of the investigator.

Study discontinuation occurs when an enrolled patient ceases to participate in the study, regardless of the reason (as detailed under "Follow-up" in Section 3.2.8). Patients have the right to withdraw consent at any time; if this is the case, no further follow-up should be performed.

The date and reason for study discontinuation will be clearly documented on the patient's CRF.

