6.7.1. General rules for dose modification

6.7.1.1. DURVALUMAB

Management of toxicity is described in appendix 4.

Reactions may occur during or after the infusion of study medication. The reaction may cause fever or chills and a change in blood pressure or difficulty in breathing.

In the event of a \leq Grade 2 infusion-related reaction, the infusion rate of study drug may be decreased by 50% or interrupted until resolution of the event (up to 4 hours) and re-initiated at 50% of the initial rate until completion of the infusion. For subjects with a \leq Grade 2 infusion-related reaction, subsequent infusions may be administered at 50% of the initial rate. Acetaminophen and/or an antihistamine (e.g., diphenhydramine) or equivalent medications per institutional standard may be administered at the discretion of the investigator.

If the infusion-related reaction is Grade 3 or higher in severity, study drug will be discontinued.

The standard infusion time is one hour, however if there are interruptions during infusion, the total allowed time from infusion start to completion of infusion should not exceed 4 hours at room temperature, with maximum total time at room temperature not exceeding 4 hours (otherwise requires new infusion preparation).

As with any antibody, allergic reactions to dose administration are possible. Appropriate drugs and medical equipment to treat acute anaphylactic reactions must be immediately available, and study personnel must be trained to recognize and treat anaphylaxis. The study site must have immediate access to emergency resuscitation teams and equipment in addition to the ability to admit subjects to an intensive care unit if necessary.

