9.2. Definition of study populations

9.2.1. Phase I (Dose escalation part)

The following patients will not be included in the population assessable for safety (primary analysis) and thus will be replaced:

- Patients who received \leq 75% RDI (Relative Dose Intensity) for trabectedin OR \leq 75% RDI for durvalumab over cycle 1, due to drug-related AE not considered as DLT.
- Patients who goes off treatment over cycle 1 for reasons unrelated to toxicity (DLT or any other AE), e.g. progression, lost to follow-up, will be replaced

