	Grade 2	
Hold study drug/study regimen dose until Grade 2 resolution to \leq Grade 1
 
 • If toxicity worsens then treat as Grade 3 or Grade 4 • If toxicity improves to Grade \leq 1 then the decision to reinitiate study drug/regimen will be based upon treating physician's clinical judgment and after completion of steroid taper. 
Study drug/study treatment can be resumed at the next scheduled dose once event stabilizes to grade \leq 1 and 5-7 days have passed after completion of steroid taper
	
For Grade 2
 
 - Monitor symptoms daily and consider hospitalization - Obtain Pulmonary and Infectious Diseases Consults; consider discussing with Clinical Study Lead, as needed - Promptly start systemic steroids (e.g., prednisone 1 to 2mg/kg/day PO or IV equivalent) - Reimaging as clinically indicated, consider Chest CT with contrast and repeat in 3-4 weeks - If no improvement within 2 to 3 days, additional workup should be considered and prompt treatment with IV methylprednisolone 2 to 4mg/kg/day started - If no improvement within 2 to 3 days despite IV methylprednisolone at 2 to 4 mg/kg/day, promptly start immunosuppressive therapy such as tumor necrosis factor (TNF) inhibitors (e.g. infliximab at 5 mg/kg IV once, may be repeated at 2 and 6 weeks after initial dose at the discretion of the treating provider or relevant practice guidelines). Caution: It is important to rule out sepsis and refer to infliximab label for general guidance before using infliximab - Consider as necessary discussing with Clinical Study Lead
	Grade 3 or 4	Permanently discontinue study drug/study regimen	
For Grade 3 or 4
 
 - Promptly initiate empiric IV methylprednisolone 1 to 4 mg/kg/day or equivalent - Obtain pulmonary and infectious disease consults; consider, as necessary, discussing with Clinical Study Lead. - Hospitalize the patient - Supportive Care (e.g. oxygen) - If no improvement within 2 to 3 days, additional workup should be considered and prompt treatment with additional immunosuppressive therapy such as TNF inhibitors (e.g. infliximab at 5 mg/kgIV, may be repeated at 2 and 6 weeks after initial dose at the discretion of the treating provider or relevant practice guidelines) started. Caution: rule out sepsis and refer to infliximab label for general guidance

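### The DLT definition names neither grade 5 nor the cycle 1 toxicities the protocol makes permanent stops whatever their duration, so such patients can count as DLT-free or be replaced

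*Protocol*

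**What the plan says.** **DLT definition** (protocol synopsis, 3.2 and 8.1; SAP synopsis). The event must meet "Begins on the first 21 days of treatment", be at least possibly related, and satisfy one of five criteria:
- "Any grade-4 toxicity (except for vomiting without maximal symptomatic/prophylactic treatment", with a conditional exception for transaminitis;
- "Grade-3 non-haematological toxicity lasting > 7days", with exceptions for a first episode of nausea and for transaminitis;
- grade 3 haematological toxicity lasting more than 7 days;
- grade 4 neutropenia with fever;
- thrombocytopenia above grade 2 with bleeding.

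**Stopping rules.** Protocol 4.4 lists "Grade ≥ 3 infusion reaction" among the reasons for ending treatment, and 6.7.1.1 says "If the infusion-related reaction is Grade 3 or higher in severity, study drug will be discontinued". Appendix 4, which 6.7 and 6.7.2 apply, has the instruction "Permanently discontinue study drug/study regimen" for grade 3 or 4 pneumonitis. It gives the same instruction at grade 3 for nephritis, acute pancreatitis, neurotoxicity, myocarditis and infusion reactions. None of these depends on duration.

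**Analysis population.** Protocol 9.2.1 and SAP 2.3 exclude and replace a patient who received 75% or less of the relative dose intensity (RDI) of either drug over cycle 1 "due to drug-related AE not considered as DLT". They also replace patients who leave treatment in cycle 1 for reasons unrelated to toxicity.

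**Safeguards.** The steering committee meets before each escalation and resolves DLT status issues (3.2, 3.3.2, 11.1.1). The IDMC is asked to approve the MTD before expansion (11.1.2). The DLT form has a field OTH_DLT, without a definition (SAP 3.2.3). Datalisting 2 (SAP 4.1.2) shows DLT status, maximum intensity and treatment modification for each adverse event.

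**The concern.** The same protocol treats an event as grave enough to bar further treatment and yet, if it lasts 7 days or less, as not dose-limiting. The population rules compound this: depending on how much drug was given, the patient either counts as a tolerating patient or leaves the count. In both cases the toxicity does not weigh against the dose.

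In cohorts of three to six, one patient can change the decision. An MTD set this way is biased upward for the toxicities concerned, and all 30 expansion patients are to be treated at that MTD. Grade 5 is a smaller, literal gap: the first criterion says grade 4, not grade 4 or higher.

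**Working it through.** The plan attaches no figure to the DLT definition. The nearest one, 18 assessable patients in the escalation part, reproduces as 3 levels × 6. The check is therefore a trace of the rules, followed by an illustration of size.

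**Step 1. Trace individual patients.** Trabectedin is given on day 1 and durvalumab on day 2, so a stop after day 2 leaves cycle 1 RDI intact.

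| Related event in cycle 1 | Listed DLT? | Population status |
|---|---|---|
| Grade 3 pneumonitis, nephritis, pancreatitis, neurotoxicity or myocarditis, 7 days or less, after full doses; permanent stop | No | The exit is due to toxicity, so 9.2.1 does not replace the patient: assessable, DLT-free |
| Grade 3 infusion reaction, 7 days or less, more than 75% of durvalumab given | No | As above |
| Same reaction, 75% or less of durvalumab given | No | Excluded and replaced |
| Fatal event with no listed DLT recorded first | Not named; only the thrombocytopenia criterion is open-ended upward | Depends on the end-of-treatment code |

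The SAP 2.3 program agrees with the first two rows. An exit within 21 days without a DLT is set to not assessable only if the reason code is neither 4 nor 12. SAP 2.4 labels code 12 as progression with adverse event. Code 4 is not labelled; I assume it means adverse event.

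**Step 2. Effect on one cohort of three (no assumed rate).** The events are those in the first two rows, with no other DLT.

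| Such events in 3 patients | Reading as written | Reading if counted as DLTs |
|---|---|---|
| 1 | 0/3: next dose level | 1/3: at least 3 more at this level |
| 2 | 0/3: next dose level | 2/3: escalation stops |

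If the patient is replaced instead, the event leaves the count and the replacement's outcome takes its place.

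**Step 3. Probability of escalating (assumed rates).** Under the 3+3 rule a level is passed with 0/3, or with 1/3 followed by 0/3:

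P(escalate) = (1−p)³ + 3p(1−p)² × (1−p)³

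Assume DLTs as defined occur in 15% of patients, and add a share s with a permanent stop that is not a listed DLT. The documents give no rate of s for the combination. Protocol 1.4.3 reports treatment-related permanent discontinuation of durvalumab monotherapy in 18 of 694 subjects (2.6%) over all treatment. That brackets s from above on those data only, because not all such stops fall in cycle 1 and some would be DLTs. The value 1% is an assumption.

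- As written, p = 0.15: 0.614 + 0.200 = 0.814, or 81%.
- s = 1% counted, p = 0.16: 0.593 + 0.201 = 0.793, or 79%.
- s = 2.6% counted, p = 0.176: 0.559 + 0.201 = 0.760, or 76%.
- Sensitivity only, s = 5% or 10%, p = 0.20 or 0.25: 71% or 60%.

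Replacing the 2.6% rather than counting them DLT-free barely changes the first line: p = 0.15/0.974 = 0.154 gives 0.605 + 0.200 = 0.806, again about 81%.

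**The case against.** **Escalation is not automatic.** The steering committee reviews every step and can rule on DLT status, consulting an oncologist who did not treat the patient where needed. The IDMC reviews the MTD, the RP2D draws on all safety data, OTH_DLT suggests that DLTs outside the list can be recorded, and Datalisting 2 would show the events. This lowers the practical risk. But none of these provisions contains a criterion, and none overrides the replacement rule: they allow a correction without requiring one.

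**Stopping rules and DLT criteria serve different ends.** Tolerating brief, reversible grade 3 events is a legitimate choice. Durvalumab is given at a fixed dose, so charging an infusion reaction to a trabectedin level is debatable. That is a reason to state the decision, since the text is silent on events after which the protocol itself bars re-treatment.

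**Appendix 4 calls itself a recommendation.** It does, but 6.7 and 6.7.2 apply it, and the infusion-reaction stop stands in the body of the protocol.

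**The 7-day criterion has two readings.** It may mean the time at grade 3 or the duration of the whole toxicity. On the second reading, an event that falls to grade 2 but persists beyond 7 days is a DLT, which narrows the gap without closing it.

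**Grade 5 is literalism.** A committee would almost certainly count a related death. I agree that this is the minor part.

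**The events are rare.** Pneumonitis is not among the related grade 3 or higher events listed for 3 or more of the 694 monotherapy subjects, so it occurred in at most 2 (0.3%). This limits the likely size, though the combination's rates are unknown.

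**Conclusion.** The gap is real on the text, and its direction is clear: it can only make a dose look better tolerated than under a definition that counts these events. Its size is unknown for the combination. Under the assumptions shown it is modest, 81% against 79% to 76%. The 71% and 60% figures are sensitivity values with no support in the documents for cycle 1.

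A reader might infer three stronger things that the documents do not support:
- **That a cohort with two grade 3 pneumonitis cases in three patients is a realistic route to a wrong escalation.** At 2 of 694 or fewer, the chance is about 3 × (2/694)² = 0.000025 on the monotherapy data.
- **That the 9.4% of related grade 3 or higher events in protocol 1.4.3 measures the problem.** It covers all treatment and includes fatigue, liver enzyme rises and events of grade 4 and above. Likewise, the 1.7% toxic deaths in 1.3.3 are for single-agent trabectedin under three schedules.
- **That capillary leak syndrome belongs on the list.** Section 6.7.1.2 says only to discontinue trabectedin; it does not say permanently and does not mention the regimen.

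The point merits a correction of wording and counting. It does not show that the escalation design fails.

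**What to change.** 1. Reconcile the DLT definition (both synopses, protocol 3.2 and 8.1) with 4.4, 6.7.1.1 and Appendix 4. State the DLT status of grade 5 and of every related day 1 to 21 event for which those sections mandate permanent discontinuation. Which events count is for the sponsor and steering committee to decide. Say also whether the 7 days refer to time at grade 3 or to the whole toxicity.
2. Amend protocol 9.2.1 and SAP 2.3, text and program, so that no patient permanently stopped for related toxicity in cycle 1 is replaced or counted DLT-free until the steering committee has ruled on DLT status. Label the end-of-treatment reason codes.
3. Add to the dose-level report a count of cycle 1 permanent discontinuations for toxicity beside the DLT count.

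The cost is a few sentences, a small program change and one summary count from data already collected on the adverse event and end-of-treatment forms. Sections 3.2 and 8.1 already differ on the nausea exception, so this wording needs revision anyway. The downside is that escalation may stop slightly earlier.

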3.3. Dose escalation part

3.3.1. Treatment scheme

Trabectedin will be administered intraveinously, on day 1 of each cycle, every three weeks, as appropriate for assigned dose level.

Durvalumab will be administered intraveinously, at fixed doses of 1120 mg (equivalent to 15 mg/kg), on day 2 of each cycle, every three weeks.

A treatment cycle consists of 3 weeks. Treatment may continue until disease progression or study discontinuation (withdrawal of consent, intercurrent illness, unacceptable adverse event or any other changes unacceptable for further treatment, etc.).

3.3.2. Dose levels

Dose escalation study assessing 3 doses level of Trabectedin given in combination with durvalumab (fixed dose).

Level	-1	1	2	3
Trabectedin (3h)	0.8 mg/m ²	1 mg/m ²	1.2 mg/m ²	1.5 mg/m ²

- The starting dose of Trabectedin is 1 mg/m².
- The maximum dose of Trabectedin administered (1.5 mg/m²) will not be exceeded.
- Patients will be allocated to 3 doses levels following a 3 + 3 design.
- A minimum of 3 patients and a maximum of 6 patients will be entered on each dose level.
- All 3 patients within a dose level will be observed during 21 days (the period of observation of DLTs) before accrual to the next higher dose level may begin.
- Dose escalation will proceed according to the following scheme:

Number of patients with DLT at one dose level	Escalation Decision Rule
0 out of 3	Enter 3 patients at the next dose level.
≥2	Dose escalation will be stopped. This dose level will be declared as the maximum administered dose (MAD). Three additional patients will be entered at the next lowest dose level if only 3 patients were treated previously at that dose.
1 out of 3	Enter at least 3 more patients at this dose level. 
• If 0 of these 3 patients experience DLT, proceed to the next dose level.• If 1 or more of this group suffer DLT, dose escalation will be stopped, and this dose is declared as the MAD. Three additional patients will be entered at the next lowest dose if only 3 patients were treated previously at that dose.
≤1 out of 6	This will be the maximum tolerated dose (MTD).

- As described above, the maximum administered dose (MAD) for Trabectedin is the dose in which ≥2/3 or ≥2/6 patients experience DLT.

- If the MAD for Trabectedin is seen at the starting dose level, then dose level “-1” will be the recommended dose.
- The MTD for Trabectedin is defined as the highest dose at which no more than 1 in 6 of the patients in the cohort experienced a DLT during the period of observation of DLTs.
- The steering committee will meet before proceeding or not to each dose escalation. In addition, the steering committee will be consulted to resolve any specific question regarding the DLT status (see section 12.1.1).
- Conclusions of the steering committee for the definition of MTD will be submitted for approval to an independent data monitoring committee (IDMC) before opening the expansion cohorts.

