Number of patients with DLT at one dose level	Escalation Decision Rule										
0 out of 3	Enter 3 patients at the next dose level.										
≥ 2	Dose escalation will be stopped. This dose level will be declared as the maximum administered dose (MAD). Three additional patients will be entered at the next lowest dose level if only 3 patients were treated previously at that dose.										
1 out of 3	
Enter at least 3 more patients at this dose level.
 
 If 0 of these 3 patients experience DLT, proceed to the next dose level. If 1 or more of this group suffer DLT, dose escalation will be stopped, and this dose is declared as the MAD. Three additional patients will be entered at the next lowest dose if only 3 patients were treated previously at that dose. 										
≤ 1 out of 6	This will be the maximum tolerated dose (MTD).										
	
 As described above, the maximum administered dose (MAD) for Trabectedin is the dose in which $\geq 2/3$ or $\geq 2/6$ patients experience DLT. If the MAD for Trabectedin is seen at the starting dose level, then dose level “1” will be the recommended dose. The MTD for Trabectedin is defined as the highest dose at which no more than 1 in 6 of the patients in the cohort experienced a DLT during the period of observation of DLTs. The steering committee will meet before proceeding or not to each dose escalation. In addition, the steering committee will be consulted to resolve any specific issue regarding the DLT status. Conclusions of the steering committee for the definition of MTD will be submitted for approval to an independent data monitoring committee (IDMC) before opening the expansion cohorts. 										
	
EXPANSION COHORT
 
Once the MTD has been defined, the expansion cohorts will be opened. All patients will be treated at the MTD of Trabectedin (as defined in the dose escalation trial) given in association with Durvalumab with the same schedule as in the dose escalation trial. Following the expansion cohorts, the RP2D for Trabectedin will be identified by the steering committee based on safety data from patients included in the dose escalation part and the expansion cohorts, as well as PD data. Data from all patients (escalation + expansion cohorts) will be used to define the RP2D.
										

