3.4. EXPANSION cohorts

- Once the MTD has been defined based on the dose escalation study, the expansion cohorts will be opened. All patients will be treated at the MTD of Trabectedin (as defined in the escalation trial) given in association with durvalumab with the same schedule as in the phase I trial.
- Following the expansion cohorts, the RP2D for Trabectedin will be identified by the steering committee based on safety data from patients included in the dose escalation part and the expansion cohorts, as well as PD data. Data from all patients (escalation + expansion cohorts) will be used to define the RP2D.

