Level	-1	1	2	3							
Trabectedin (3h)	0.8 mg/m ²	1 mg/m ²	1.2 mg/m ²	1.5 mg/m ²							

	
 observation of DLTs) before accrual to the next higher dose level may begin. Dose escalation will proceed according to the following scheme: 
  
 Number of patients with DLT at one dose level	Escalation Decision Rule	
   
 0 out of 3	Enter 3 patients at the next dose level.	
 
 ≥ 2	Dose escalation will be stopped. This dose level will be declared as the maximum administered dose (MAD). Three additional patients will be entered at the next lowest dose level if only 3 patients were treated previously at that dose.	
 
 1 out of 3	 Enter at least 3 more patients at this dose level. 
 If 0 of these 3 patients experience DLT, proceed to the next dose level. If 1 or more of this group suffer DLT, dose escalation will be stopped, and this dose is declared as the MAD. Three additional patients will be entered at the next lowest dose if only 3 patients were treated previously at that dose. 	
 
 ≤ 1 out of 6	This will be the maximum tolerated dose (MTD).	
  
 
 As described above, the maximum administered dose (MAD) for Trabectedin is the dose in which $\geq 2/3$ or $\geq 2/6$ patients experience DLT. If the MAD for Trabectedin is seen at the starting dose level, then dose level "-1" will be the recommended dose. The MTD for Trabectedin is defined as the highest dose at which no more than 1 in 6 of the patients in the cohort experienced a DLT during the period of observation of DLTs. The steering committee will meet before proceeding or not to each dose escalation. In addition, the steering committee will be consulted to resolve any specific issue regarding the DLT status. Conclusions of the steering committee for the definition of MTD will be submitted for approval to an independent data monitoring committee (IDMC) before opening the expansion cohorts. 	Number of patients with DLT at one dose level	Escalation Decision Rule	0 out of 3	Enter 3 patients at the next dose level.	≥ 2	Dose escalation will be stopped. This dose level will be declared as the maximum administered dose (MAD). Three additional patients will be entered at the next lowest dose level if only 3 patients were treated previously at that dose.	1 out of 3	Enter at least 3 more patients at this dose level. 
 If 0 of these 3 patients experience DLT, proceed to the next dose level. If 1 or more of this group suffer DLT, dose escalation will be stopped, and this dose is declared as the MAD. Three additional patients will be entered at the next lowest dose if only 3 patients were treated previously at that dose. 	≤ 1 out of 6	This will be the maximum tolerated dose (MTD).

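### If the starting dose is the MAD, level -1 becomes the recommended dose with no requirement that it be tested or meet the 1-in-6 DLT criterion

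*Protocol*

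**What the plan says.** Protocol section 3.3.2 lists four trabectedin levels: -1 (0.8 mg/m²), 1 (1 mg/m², the starting dose), 2 (1.2 mg/m²) and 3 (1.5 mg/m²). A level is the MAD when at least 2 of 3 or at least 2 of 6 patients have a DLT. For the case where this happens at the starting dose, the section says: "If the MAD for Trabectedin is seen at the starting dose level, then dose level “-1” will be the recommended dose". The SAP synopsis (Study design, dose escalation part) has the same rule. The protocol synopsis, in the text supplied, reads "If the MAD for Trabectedin is seen at the starting dose level, then dose level “1” will be the recommended dose".

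Four other provisions bear on this branch:

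- MTD, section 3.2: "The MTD is defined as the highest dose at which no more than 1 in 6 patients in the cohort experience a DLT". Section 3.3.2 repeats the definition immediately after the fallback sentence.
- De-escalation, section 3.3.2, the row for 2 or more DLTs: "Three additional patients will be entered at the next lowest dose level if only 3 patients were treated previously at that dose".
- Recommended phase II dose (RP2D), section 3.2: "The RP2D dose corresponds to the dose level to be recommended for further investigations in phase II trials", and "Data from all patients (dose escalation trial and expansion cohorts) will be used to define the RP2D". Section 3.4 fixes the timing: "Following the expansion cohorts, the RP2D for Trabectedin will be identified by the steering committee".
- Expansion, sections 3.3.2 and 3.4: the cohorts open once an MTD has been defined, patients are treated at that MTD, and the IDMC must first approve the steering committee's MTD conclusion.

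The SAP body (sections 2.3, 3.2.1 and 3.2.3) defines the population and the descriptive DLT summaries. It adds no decision rule for level -1.

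**The concern.** The fallback sentence is triggered by the result at level 1 alone. It attaches no DLT condition to level -1 and does not say that anyone must be treated there before it is recommended. Every other level has to earn its status through observed DLTs.

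The branch arises only if the starting dose fails, but then it is the only text written for that situation. The primary objective includes establishing the MTD and the RP2D, so a team following the sentence as written could report 0.8 mg/m² as the dose conclusion with no data at that dose, or with data that fail the protocol's own criterion. A second gap follows: if level -1 also shows 2 or more DLTs, the table's only instruction is to go one level lower. No lower level exists, and no text says outright that no MTD is declared and enrolment stops.

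**Working it through.** **1. The plan's own figure.** Protocol section 9.1.1 (dose escalation part) counts 3 dose levels with at most 6 patients each: 3 × 6 = 18 assessable, with up to 20 accrued. The 18 reproduces. It does not count level -1, which is a fourth level in the section 3.3.2 table.

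**2. Does any rule require level -1 to be tested?** Suppose level 1 is the MAD at first testing.

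- The de-escalation row adds 3 patients at the next lower level only where exactly 3 were treated before. Level -1 has had 0, so the condition is not met.
- The fallback sentence then applies and goes straight to a recommendation.
- The 3-to-6-patients-per-level sentence and the row declaring an MTD at 1 or fewer DLTs in 6 could be read to cover level -1, but neither says that patients are to be entered there.

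**3. Do the rules agree if level -1 is tested?** With 0 or 1 DLT in 6, yes. With 2 or more, the MTD definition rejects level -1 and the fallback sentence still recommends it.

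**4. How often could that happen?** The documents give no DLT rate for the combination, so the rates below are assumptions. Let p be the true rate at level 1 and q the rate at level -1.

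- P(level 1 is MAD at first testing) = P(≥2 of 3) + P(1 of 3) × P(≥1 of next 3). At p = 0.30: 0.216 + 0.441 × 0.657 = 0.506.
- P(level -1 fails in up to 6 patients) = P(≥2 of 6) = 1 − (1−q)^6 − 6q(1−q)^5. At q = 0.15: 1 − 0.377 − 0.399 = 0.224 after rounding at the end (0.2235). Stopping early at 2 of 3 does not change this total.
- Joint probability = product of the two. At 0.30 and 0.15: 0.5057 × 0.2235 = 0.113.

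| p (level 1) | q (level -1) | Level 1 is MAD | Level -1 fails | Both |
|---|---|---|---|---|
| 10% | 5% | 9.4% | 3.3% | 0.3% |
| 20% | 10% | 29.1% | 11.4% | 3.3% |
| 30% | 15% | 50.6% | 22.4% | 11.3% |
| 40% | 20% | 69.1% | 34.5% | 23.8% |

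Halving the rate for a dose cut of 20% (1 to 0.8 mg/m²) may be generous. With smaller reductions the joint figure rises: 17% at 30%/20%, 32% at 40%/25% and 64% at 50%/40%.

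**5. Patients needed if level -1 is tested.**

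- Direct route, level 1 fails at first testing: at most 6 + 6 = 12, within 18.
- Longest route: level 1 has 0 of 3 and level 2 has 0 of 3; level 3 fails with 6; level 2 is filled to 6 and fails; level 1 is filled to 6 and fails; level -1 takes 6. Total 4 × 6 = 24, above both 18 and 20.

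**The case against.** The best defence is that the rest of the protocol already supplies the outcome. The decision table is written for DLTs at any one level, so 2 or more at level -1 would make it a MAD. It would then fail the MTD definition, and under section 3.4 expansion could not open. Section 9.3 has the IDMC assess the safety data and validate the MTD, and section 11.1 gives the committees patient protection and early discontinuation for toxicity. On this view the sentence merely names the level to use next.

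Much of this stands. A reader might infer that expansion patients could be treated at a failing dose, or that the protocol has no route to an MTD at level -1 and no stop at all. The documents support neither inference: expansion requires a defined MTD and IDMC approval, and the per-level sample rule and the 1-in-6 row can be read to cover level -1.

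A reader might also say that the sentence contradicts the RP2D rule. That holds only if the undefined term recommended dose means the RP2D. If it does, the sentence pre-empts sections 3.2 and 3.4, but the sentence itself says neither MTD nor RP2D.

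The defence does not remove the wording. Committee review is not a decision criterion, and section 11.1.2 makes the IDMC's role advisory. A specific sentence that recommends a dose unconditionally still disagrees with the general definitions whenever level -1 fails, and still permits a recommendation with no patient treated there.

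Finally, the protocol synopsis as supplied names level 1, the dose just declared the MAD. Section 3.3.2 and the SAP both have -1, so a minus sign lost in PDF reading is plausible. It is a point to check against the source and does not count as an error here.

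**Conclusion.** The concern holds as a defect in a stated decision rule. If level 1 is the MAD, protocol section 3.3.2 and the SAP synopsis recommend level -1 without requiring it to be tested or to meet the at-most-1-in-6 criterion, and the de-escalation row does not close the gap. What is at risk is the dose conclusion and an explicit stop at the lowest level; the expansion cohorts stay behind the MTD definition and IDMC approval.

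The probabilities are illustrative only. They measure how often the fallback sentence and the MTD definition would give opposite answers, from 0.3% to 24% if level -1 has half the level 1 rate and level 1's rate is 10% to 40%, and more if the dose reduction helps less. They are not probabilities that a patient receives a wrong dose. The textual finding does not depend on them.

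**What to change.** In protocol section 3.3.2 and the SAP synopsis, replace the fallback sentence with:

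*If level 1 is declared the MAD, 3 patients are entered at level -1, and 3 more if 0 or 1 of 3 has a DLT, with no re-escalation to level 1. Level -1 is the MTD only if at most 1 of 6 has a DLT. With 2 or more DLTs, enrolment stops for steering committee and IDMC review, no MTD is declared and expansion does not open.*

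Make the same replacement in the protocol synopsis, after checking whether its 1 is a lost minus sign.

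The text change is one sentence in three places. If the branch is entered, level -1 costs 3 to 6 patients and one or two 21-day DLT windows plus accrual. On the direct route the total is at most 12 assessable patients, inside the planned 18 assessable and 20 accrued. It would be wrong to conclude that the sample size is unaffected on every route: arriving at level -1 after de-escalation from level 3 can take 24. Section 9.1.1 should therefore state that its 18/20 maximum does not cover that path.
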